7.3 THE LEVEL OF STATISTICAL SIGNIFICANCE

Whenever applicable, a 5% level of significance will be used.

7.4 CRITERIA FOR THE TERMINATION OF THE TRIAL.

As this is not an interventional study, the chance to terminate the trial is minimal.

7.5 PROCEDURE FOR ACCOUNTING FOR MISSING, UNUSED, AND SPURIOUS DATA.

Spurious and/or missing data will be summarised and reasons for missingness given where possible. All data analyses will be based on the complete data only.

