7. Anoxic time [total time between cardiac arrest was noted and ROSC]. If multiple episodes of cardiac arrest then the sum of all anoxic times to be considered.
8. GCS before intubation [total or with components if available]
9. Aetiology of cardiac arrest [cardiac or non-cardiac or unknown]
10. CT scan report if performed because it was clinically indicated
11. Cerebral performance category at ICU discharge and Hospital discharge.
12. Date of death, number of days post ROSC that death occurred
13. ICU length of stay, hospital length of stay
14. Time of SSEP performed [hours post ROSC]
15. Time between ROSC and ICU admission,
16. First 24 hours post ROSC: mean SpO₂, mean PaO₂, mean PaCO₂, mean HR, mean BP, mean Glucose levels, mean Lactate levels, mean pH, mean BE, Urea and Creatinine levels, liver function tests: ALT, INR, Bil and ammonia in patients with pre-admission acute or chronic hepatic dysfunction], Plasma Na levels, Temperature, SOFA Score, APACHE II score.

No particulars tests needed for the study purposes. The aforementioned tests are performed and the aforementioned clinical data are recorded for all patients admitted to Derriford ICU after out of hospital cardiac arrest as part of daily clinical practice.

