4.3 INCLUSION CRITERIA

1. All adult comatose survivors after out of hospital cardiac arrest who are admitted to Derriford Hospital Intensive Care Unit [Penrose and Pencarrow wards]. The cause of cardiac arrest may be cardiac and/or non-cardiac or unknown at the time of enrolment.
2. All patients must be comatose before intubation [GCS equal or lower than 8].
3. All patients must be on one or more invasive organ support [e.g. Endotracheal intubation and mechanical ventilation, vasopressor and/or inotropic support, Continuous Renal Replacement Therapy Sedated and/or on neuromuscular blocking agents].
4. All patients must be sedated before and during the time of SSEP recording. If clinically indicated, neuromuscular blocking agents may also be used.
5. All patients must be on targeted temperature management as per Derriford ICU policy and protocol: For the first 24 hours after ICU admission, the target-temperature is 36°C with temperature control commencing within the first hour after critical care admission. For the

next 48 hours the temperature of the patients will be maintained between 36-37°C. The aforementioned temperature targets are achieved with external cooling devices.

6. Patients must have a CT scan of the head if severe cerebral pathology which is part of the exclusion criteria is clinically suspected.
7. Absence of all exclusion criteria

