7. STATISTICS AND DATA ANALYSIS

7.1 DESCRIPTION OF STATISTICAL METHODS

Demographic information of participants will be summarized using descriptive statistics and presented in tables to provide an exploratory overview of the study population.

Continuous measures will be summarised as means, standard deviations and ranges where the distribution appears normal, and as medians, inter-quartile ranges and ranges otherwise.

Categorical data will be summarised by frequencies and percentages.

The primary outcome measure is the CPC score at hospital discharge with discrete values ranging from 1 to 5. The score will be dichotomised as 1-2 (positive or good outcome) and 3-5 (negative or poor outcome).

Sensitivity, specificity and predictive values of P25/30 in predicting poor outcome will be computed and the results compared to that of N20. Where appropriate, parameter estimates will be presented with 95% confidence intervals. Significant demographic and clinical predictors of poor neurological outcomes will be assessed and identified using regression models.

Statistical data analysis will be undertaken once data collection from the required number of participants is completed. No interim analysis is scheduled for this study.

Analyses will be performed in SPSS version 24 (or later), supplemented where required by Stata SE version 14.2 (or later) and R.

a. THE NUMBER OF PARTICIPANTS

Sample size calculation was based on diagnostic test accuracy (adequate sensitivity) of P25/30. A previous study (Kim et al. 2018) on patients treated by hypothermic targeted temperature management showed that the sensitivity of P25/30 in predicting poor outcome is 90.12% (95% CI, 81.5–95.6%). Though the proposed study will be based on those who are not treated by hypothermic targeted temperature management, the result (90%) is the 'best' available information regarding pre-determined sensitivity of P25/30. From experience of the team and analysis of the past three-years

pilot data, the prevalence of poor outcome was assumed to be 75%. In order the maximum marginal error of estimate does not exceed from 5% with 95% confidence level, and adjusting for drop-out/lack of consent at 3%, the minimum required sample size will be 115. No power was assumed in the calculation of the sample size as there is no testing of hypothesis.

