APPENDIX

Additional information to the protocol, consisting of:

- Schedule of events table
- Cerebral Performance Category
- Performance status
- Comorbidities score
- Participant/patient information sheet

TABLE 1. SUMMARY OF INVESTIGATIONS, TREATMENT AND ASSESSMENTS

Investigations / Treatments / Assessments	Time performed / recorded		
	At enrolment [First 24 hours post ROSC]	ICU discharge	Hospital Discharge
History of Present Complaint and Past medical History	X		
Neurological examination	X	X	X
ECG	X		
Cardiac arrest Rhythm	X		
CXR	X		
FBC, Creatinine-U&E, LFT, INR, Ammonia [if acute or chronic hepatic dysfunction], mean Glucose levels, mean Lactate levels	X		
Mean SpO ₂ , mean PaO ₂ , mean PaCO ₂	X		
Mean HR, mean BP, mean T			
APACHE II score	X		
SOFA score	X		
Cerebral Performance Category		X	X
ECOG / WHO pre-admission performance status	X		
Charlson Comorbidity Index Scoring System	X		
Informed consent	X		

FIGURE 1. THE CEREBRAL PERFORMANCE CATEGORY SCALE [CPC]

Cerebral Performance Category [CPC] Scale	
Positive [good] Neurologic Outcomes	CPC 1: Full Recovery or Mild Disability
	CPC 2: Moderate Disability but Independent in Activities of Daily Living
Negative [poor] Neurologic Outcomes	CPC 3: Severe Disability – Dependent in Activities of Daily Living
	CPC 4: Persistent Vegetative State
	CPC 5: Death

FIGURE 2. THE ECOG/WHO PERFORMANCE STATUS SCORE

ECOG/WHO Performance Status score	
Grade	Performance status
0	Fully active, able to carry on all pre-disease performance without restriction
1	Restricted in physically strenuous activity but ambulatory and able to carry out work of a light or sedentary nature e.g. light house work, office work
2	Ambulatory and capable of all self-care but unable to carry out any work activities. Up and about more than 50% of waking hours
3	Capable of only self-limited care, confined to bed or chair more than 50% of waking hours
4	Completely disabled. Cannot carry on any self-care. Totally confined to bed or chair
5	Dead

FIGURE 3. THE CHARLSON COMORBIDITY INDEX SCORING SYSTEM

Charlson Comorbidity Index Scoring System	
Score	Condition

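### The complete-data-only rule in Section 7.5 could needlessly drop patients from the secondary regression and multimodal models, where CT report and ammonia exist only on clinical indication

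*Combined protocol and SAP*

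**What the plan says.** Section 7.5 has two sentences. The first is descriptive: "Spurious and/or missing data will be summarised and reasons for missingness given where possible". The second sets the rule: "All data analyses will be based on the complete data only". The section does not say whether complete means complete for the analysis at hand or for every collected variable. It names no imputation and no sensitivity analysis.

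Two secondary analyses use covariates. Section 7.1 says: "Significant demographic and clinical predictors of poor neurological outcomes will be assessed and identified using regression models". It gives no covariate list, model size or selection rule. Section 3.1 makes the comparison of N20-based and P25/30-based multimodal prognostic models a secondary endpoint.

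In the data list of Section 4.1, two possible predictors are conditional. Item 10 is "CT scan report if performed because it was clinically indicated", and item 16 includes "ammonia in patients with pre-admission acute or chronic hepatic dysfunction". Table 1 in the Appendix repeats the ammonia condition, and inclusion criterion 6 in Section 4.3 requires a head CT only on clinical suspicion.

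Three other places bear on the point. Section 4.1 closes its list by saying that these data are recorded routinely for all such patients. Section 7.7 includes all eligible participants. Section 7.6 makes a separate SAP optional.

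**The concern.** A complete-case rule suits the accuracy tables, which need two things per patient: a readable SSEP and a CPC. It suits the regression less well, because one missing covariate removes the whole patient.

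For CT and ammonia the gaps are structural. A patient without an indication has no value, and none was ever meant to exist. Applied to a model with either item, the rule would keep only patients whose clinicians had a reason to scan, or who had liver disease. CT is a natural candidate: Section 4.1 counts imaging among the unit's multimodal prognostic inputs, and the CT report is the only imaging result in the data list.

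For other covariates the gaps would be sporadic, but they add up across a model, and the cohort has few good outcomes to lose. At stake are the precision of the secondary models and whether they describe the same patients as the accuracy results.

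**Working it through.** The plan gives no missingness rate and no expected size for the regression set, so there is no figure on this point to reproduce.

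**Inputs from Section 7 (the number of participants):** minimum sample size 115, drop-out or lack of consent 3%, poor outcome 75%. I take 115 as stated. The usual precision formula does not return it: 1.96² × 0.90 × 0.10 / 0.05² = 138.3 poor outcomes; 138.3 / 0.75 = 184.4; 184.4 / 0.97 = 190.1. That is a separate matter, and nothing below depends on it.

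**Starting set.** 115 × 0.97 = 111.55, about 112 patients. Good outcomes: 111.55 × 0.25 = 27.9, about 28. With the 120 patients of Section 3 the figures would be 116.4 and 29.1.

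**Sporadic gaps (rates assumed).** With k covariates, each missing independently in a share m of patients, the complete share is (1 − m)^k. The good-outcome share is held at 25%.

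| k | m | Complete share | Patients | Good outcomes |
|---|---|---|---|---|
| 5 | 2% | 0.98^5 = 0.904 | 100.8 | 25.2 |
| 5 | 5% | 0.95^5 = 0.774 | 86.3 | 21.6 |
| 10 | 2% | 0.98^10 = 0.817 | 91.1 | 22.8 |
| 10 | 5% | 0.95^10 = 0.599 | 66.8 | 16.7 |

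Independence is pessimistic. If all gaps fell in the same patients, the loss would be m alone, leaving 111.55 × 0.98 = 109.3 or 111.55 × 0.95 = 106.0 patients. Real gaps would lie in between.

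**Effect on precision.** Standard errors scale roughly with one over the square root of the retained share. For 10 covariates: 1/√0.817 = 1.11 and 1/√0.599 = 1.29, so 11% to 29% larger than with fully observed data. Imputation would recover part of this, not all.

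**Indication-only items (shares assumed).** Retained patients = 111.55 × share with the item.
- CT done in 30% to 90%: 33.5 to 100.4 patients, 8.4 to 25.1 good outcomes.
- Ammonia measured in 5% to 20%: 5.6 to 22.3 patients, 1.4 to 5.6 good outcomes.

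These apply only if the item enters the model and patients without it are treated as incomplete. Coding them as not performed removes this loss.

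**The case against.** The plan never says that CT or ammonia enters a model. The collection list is not a covariate list, and Section 4.1 says the data are recorded for all patients. With a few routine covariates the loss may be modest: five at 2% missing keep 90%. The primary objectives do not rest on the regression. All of this stands, and it is why the point is conditional. The general statement about routine recording does not, however, override the conditions attached to CT and ammonia in the same list.

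A reader might infer more than the documents support:

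- *That the regression will run on a small part of the cohort.* This needs a large model or one of the conditional items. Twenty covariates at 2% to 5% missing would leave 67% to 36%, but 28 good outcomes for 20 covariates is 1.4 each, a model the plan does not propose.
- *That many items are missing by design.* Two clear candidates are. GCS components are optional, but a GCS of 8 or lower is an entry criterion in Section 4.3, so the total should exist.
- *That one missing laboratory value removes a patient from the accuracy tables.* The wording allows it, but date of death is also a collected item, so on that reading every survivor would be dropped. That cannot be meant.
- *That coefficients will be biased because unwitnessed arrests have unknown details.* The documents do not describe this mechanism. Section 4.1 times anoxia from when the arrest was noted, and unwitnessed is itself a recorded value. Where missingness depends only on covariates in the model, complete-case coefficients need not be biased. Bias would arise if missingness depended on outcome given those covariates, which is possible but not shown.

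**Conclusion.** The point holds in a limited form. The complete-data rule could discard patients unnecessarily from the secondary regression and multimodal models. For 10 covariates each independently missing in 2% to 5% of patients, about 91 to 67 of 112 patients and 23 to 17 of 28 good outcomes would remain, and fewer would be lost if gaps cluster. A complete-case model with CT or ammonia would be confined to a clinically selected subset whose size the documents do not allow one to fix.

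The main harm is lost precision and a regression population that differs from the accuracy population. The size rests on assumed missingness rates, on 115 as the starting number, on 75% poor outcome, and on covariates that Section 7.1 leaves open. The primary accuracy results are untouched on a sensible reading. This is a cheap improvement of low severity.

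**What to change.** Replace the second sentence of Section 7.5 with a rule set per analysis:

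1. Accuracy analyses use every participant with a readable SSEP and a CPC, whatever covariates are missing. This also shows how Section 7.5 fits with Section 7.7.
2. Items collected only on indication (CT report, ammonia) are not imputed. They are coded as not performed or left out of the main model.
3. Sporadically missing covariates in the regression models are multiply imputed, with the outcome, N20 and P25/30 in the imputation model. Complete-case results are reported as a sensitivity analysis.

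Keep the existing commitment to summarise missing data with reasons.

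The cost is one paragraph and a little more analysis work, in the software Section 7.1 already names. The downside is reliance on a missing-at-random assumption, which is different from the assumption behind complete-case analysis and not weaker than it. That is the reason to report both. The change should be made before the data are merged, so that the choice of covariates and patients is not made after the results are seen.

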7.6 PROCEDURES FOR REPORTING ANY DEVIATION(S) FROM THE ORIGINAL STATISTICAL PLAN

Statistical analysis of the data will be performed at the end of the study as per Section 7.1 above. If deemed necessary, a separate statistical analysis plan (SAP) can be prepared prior to the completion of the study and approved by the oversight committee. The study team will discuss any deviation from the analysis plan and report it to the oversight committee. Any revisions to the SAP will be documented, including a brief justification and timing of revision.

7.7 INCLUSION IN ANALYSIS

All eligible participants will be included in the analyses.

8. ARCHIVING

Data and all appropriate documentation will be stored on safe databanks as described [on section 4.1] and will be kept for a minimum of 5 years after the completion of the study. After that period of time all data will be deleted. Similarly the data will be immediately deleted if any of the study participants or their NOK who have provided informed consent to participate in the study decides retrospectively to withdraw from the study.

9. REGULATORY ISSUES

9.1 ETHICS APPROVAL

The Chief Investigator had applied for approval from the Health Research Authority [HRA] and the North West – Haydock Research Ethics Committee. The study has been approved by the HRA and the North West – Haydock Research Ethics Committee. The Investigator will ensure that this study is conducted in full conformity with relevant regulations and with UK Policy Framework for Health and Social Care Research (2017), which have their basis in the Declaration of Helsinki.

9.2 CONSENT

Consent to enter the study must be sought from each participant only after a full explanation has been given, an information leaflet offered and time allowed for consideration. Signed participant consent should be obtained. The right of the participant to refuse to participate without giving reasons must be respected. All participants are free to withdraw at any time from the protocol treatment without giving reasons and without prejudicing further treatment. In these cases the participants remain within the study for the purposes of follow-up and data analysis.

However, all the patients enrolled in the study are expected to be in coma at the time of enrolment. This is a reality about most of the ICU patients. Therefore, within the first 24 hours after ICU admission, the members of the study group will discuss with the next of kin of the patients regarding the potential participation in the study and the informed consent process.

During this process, the members of the study group will actively listen to the thoughts of the next of kin and other family members if available and they will try to provide the maximum information to them not only about the study but also about the general potential benefit for the patients by research, the importance of the research in modern medicine and specifically in the specialty of Intensive Care Medicine where many clinical and prognostic uncertainties still exist.

The next of kin for each potential participant would be asked to consent for the participation of the patients to the study after being fully informed, both verbally and by the provision of the relevant relatives' information booklet that can be found in the appendix of this document.

Also, with the help of their next of kin for each one of the potential participants – before their enrolment in the study – we will explore the potential participants' likely previously expressed wishes or thoughts or opinions about the importance of medical research and the participation in medical research for the benefit of the patients.

If the participants in the study regain full mental capacity to provide informed consent and make informed decisions after their enrolment in the study, then they will be fully informed about the study by a member of the study group and they will be asked if they agree to continue with their participation in the study. If the participants are happy to remain in the study cohort then their data will be used for analysis and publication purposes. If they decide anytime to withdraw from the study then their decision will be respected but it will be explained that that their data already collected may still be analysed as part of the study.

The same options will be available for the next of kin that would have consented initially for the participation of patients in the study. Similarly, if the next of kin at any point before the completion of the study decided to withdraw their initial consent, then their decision would be respected but it will be explained that that the patients data already collected may still be analysed as part of the study.

The study group would be responsible to keep each one of the next of kin and/or the patients aware about the results of the study and the relevant publications [abstracts in conferences and scientific manuscripts in journals]. At that point the study group will invite the next of kin and or the participants to provide their constructive feedback about the results of the study and their feelings with regards to their participation in this study. This could be an effective way to maximise the participation and involvement of the participants to the research process, from the initial discussion and consent to the results of the research study and their feedback.

Also, that kind of interaction with the next of kin and/or the patients would give the opportunity to the members of the study group to actively explore the perspectives of the participants in their study, to maximise their experience and ultimately to help them developing their research performance by integrating useful learning points from the participants' constructive feedback to the design and practical application of their future research projects.

The aforementioned process would potentially involve the participants of this study to the dynamic development of the research process in general.

9.3 CONFIDENTIALITY

The Chief Investigator will preserve the confidentiality of participants taking part in the study and will comply with the Data Protection Act (2018).

9.4 INDEMNITY

This is an NHS-sponsored research study. If an individual suffers negligent harm as a result of participating in the study, NHS indemnity covers NHS staff and those people responsible for conducting the trial who have honorary contracts with the relevant NHS Trust. In the case of non-negligent harm, the NHS is unable to agree in advance to pay compensation, but an *ex-gratia* payment may be considered in the event of a claim.

This study is non-interventional and therefore no risk for potential harm of the participants is expected to be associated with this study

9.5 SPONSOR

University Hospitals Plymouth NHS Trust will act as the main sponsor for this study.

9.6 FUNDING

There is funding from the University Hospitals Plymouth NHS Trust Charitable Funds for £2,300 for the cost of statistical analysis.

9.7 AUDITS

The study may be subject to audit and monitoring by University Hospitals Plymouth NHS Trust under their remit as sponsor and other regulatory bodies to ensure adherence to the study protocol and the UK Policy Framework for Health and Social Care Research (2017).

10. STUDY MANAGEMENT

The day-to-day management of the study will be co-ordinated through [name] and [name], from the departments of Intensive Care Medicine and Neurophysiology, respectively.

11. PUBLICATION POLICY

The interim and final results of the study will be disseminated *via* presentations at appropriate scientific meetings and conferences and publication in appropriate peer-reviewed journals.

The research findings is planned to be disseminated in the following manner:

- a) The annual meeting of the Intensive Care Society UK
- b) International meetings: European Society of Intensive Care Medicine and International Symposium in Intensive Care and Emergency Medicine
- c) Publication in a peer reviewed journal.
- d) Feedback to study participants

The study team would be responsible to keep each one of the next of kin and/or the patients aware about the results of the study and the relevant publications [abstracts in conferences and scientific manuscript in journal]. By submitting a copy of the relevant publication [accompanied by a plain English summary/explanation of the results] to each participant and/or their next of kin, the study team will invite the next of kin and/or the participants to provide constructive feedback about the results of the study and their feelings with regards to their participation in this study.

